7. STATISTICS AND DATA ANALYSIS

Data and all appropriate documentation will be stored for a minimum of 10 years after the completion of the study, including the follow-up period.

The major data will be levels of cytokines and chemokines in nasal SAM eluates.

We shall perform a test of distribution of data (Shapiro-Wilks test), although nasal levels of chemokines and cytokines are generally non parametric in distribution.

Raw Data:

We shall make plots for individual cytokines with raw data for individuals connected by lines. These “spaghetti plots” generally have different colours for different individuals.

Summary Statistics

Normal data with graphs with means and standard error of means (SEM)

Non-normal data with graphs with medians, quartiles and ranges (box-whisker)

Non-parametric tests are used to compare challenge effects with placebo at different times:
Willcoxon signed-rank test for paired and Mann-Whitney for unpaired data.

The differences from baseline and difference compared with that from placebo (active-placebo) at each time point and the differences from placebo (active-placebo) will be calculated, and the significance determined.

We shall also analyse area under the curve (AUC), by selecting specified times in the early or late phase or for the entire response.

e.g. PGD2 from 10min to 2h

e.g. for IL-4 at 4 to 8h.

A *P* value of <0.05 is considered significant.

Randomization

For the ViDAR study randomization will be supervised by the pharmacy at St Mary’s Hospital. The pharmacy will organise the packaging and have sole access to the randomization codes until the completion of all the clinical aspects of the study.

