2. STUDY OBJECTIVES

2.1 PRIMARY AND SECONDARY OBJECTIVES

- To develop a set of well-tolerated, robust and reproducible (validated) nasal challenge systems with microbial constituents and allergen. To identify biomarker signatures following different challenges.

- To document a dose response and time course to nasal challenge in terms of cytokine and chemokine release, and nasal epithelial curettage (Rhinoprobe) mRNA expression, cell influx by flow cytometry.
- To provide a set of nasal challenge methods to enable a “proof of target pharmacology” for a novel therapy or vaccine. This may also permit dosage optimisation in relation to clinical efficacy studies.
- To develop real time sampling utilising a special probe that touches the surface of the nasal lining and is linked to a mass spectrometer.

To assess nasal cytokines/chemokines in the nasal mucosa and assess levels of circadian-associated gene expression (BMAL-CLOCK genes) in curettage samples after NAC before and after Vitamin D supplementation.

3. STUDY DESIGN (See Figures above)

Group 1: Nasal challenge with TLR Agonists: This part of the study has a total of 96 subjects divided into two parts; Part A and B.

Part A: We shall have 3 cohorts of 8 healthy volunteers (4 of the 8 having atopy). There will be a separate cohort of 8 subjects for each challenge agent (MPLA, poly-ICLC, and resiquimod).

A careful incremental ascending dose tolerability study will be performed: starting with saline and then giving single doses of 10, 100, 500µg and up to 1000µg of a given challenge agent in volumes ranging from 100µl to 500µl per nostril.

Part A, N= 24

- | | |
|---------------|-------|
| a. MPLA | n = 8 |
| b. Poly-ICLC | n = 8 |
| c. Resiquimod | n = 8 |

For each challenge agent we shall initially take serial SAM samples over 8 hours, and assess the cytokine and chemokine response.

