This involves a total of 24 subjects who are allergic to grass pollen and are vitamin D insufficient. Participants are divided into 2 groups (vitamin D supplementation and placebo arms). This is a randomized, double-blind, placebo-controlled study. They will have two NAC; one before and one after supplementation. At each NAC visit, subjects will be given a single dose of Timothy grass pollen (*Phleum P5*) allergen:

The *Phleum P5* is given as 5000 SQ-U = 1µg/100µl per nostril.

After being randomized into one of the two groups they will receive their first NAC and subsequently take vitamin D3, 4000IU (n=18) or placebo (n=6) orally once daily at approximately the same time each morning until their second NAC. This second NAC will take place between 28-35 days. During both days of NAC, serial SAM samples will be taken and nasal curettage performed. Blood samples will also be taken for routine safety tests, peripheral blood mononuclear cells (PBMC) *in vitro* assays, vitamin D, calcium, cortisol, melatonin and whole blood transcriptomics (circadian-associated genes).

Part A, N=24

- A. Subjects with grass pollen allergy and insufficient Vitamin D3
 - a. Subjects taking Vitamin D3 supplementation n = 18
 - b. Subjects on placebo n = 6

Part B: Nasal challenge with allergen involves a total of 46 subjects:

This is divided into 4 groups of subjects given a single dose of Timothy grass pollen (*Phleum P5*) allergen:

The *Phleum P5* is given as 5000 SQ-U = 1µg/100µl/nostril

Subjects with hay fever out of season (n=12)

Subjects with allergic asthma out of season (n=12): half taking no anti-inflammatory drugs, half receiving combined inhaled corticosteroids and long-acting beta-agonists (ICS/LABA)

Non-atopic healthy controls (n=6)

Subjects with hay fever out of season who will trial a novel nasal special sampling probe (SSP) for real time mass spectrometry (n=16)

N= 46

- a. People with hay fever, n = 12
- b. People with allergic asthma, n = 12
- c. Healthy, non-atopic people, n = 6
- d. People with hay fever, n = 16

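### Section 7 does not say which contrast tests vitamin D in ViDAR and names no analysis adjusted for the first allergen challenge, so a within-arm before/after test is left open

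*Combined protocol and SAP*

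**What the plan says.** Section 3 (Group 3, Part A) describes ViDAR in these terms: "This is a randomized, double-blind, placebo-controlled study". Allocation is 3:1 ("Subjects taking Vitamin D3 supplementation n = 18", with 6 on placebo). On the challenges it says: "They will have two NAC; one before and one after supplementation". They are 28 to 35 days apart.

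The ViDAR objective in Section 2.1 is to assess nasal mediators, and circadian-associated gene expression "in curettage samples after NAC before and after Vitamin D supplementation". It names no comparison between arms.

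Section 7 has no analysis paragraph for ViDAR; its only ViDAR text concerns randomisation. The general text says: "Non-parametric tests are used to compare challenge effects with placebo at different times", followed by "Willcoxon signed-rank test for paired and Mann-Whitney for unpaired data". The next sentence plans "The differences from baseline and difference compared with that from placebo (active-placebo) at each time point", with significance to be determined. A P "value of <0.05 is considered significant". No baseline-adjusted model appears.

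**The concern.** A trial with a randomised control arm and a pre-treatment measurement of the same response has a natural analysis: compare the arms on the second response, adjusted for the first. Section 7 does not name it, and it does not say which of its two tests carries the vitamin D conclusion.

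Two things are at stake. The first is validity. The test that best matches the before-and-after wording of the objective is a paired test within the vitamin D arm. That test responds to anything that differs between visits, such as a carry-over from the first challenge or assay drift. Because 18 subjects are far more likely than 6 to reach significance, the pattern of significant on vitamin D but not on placebo can arise when both arms have moved by the same amount.

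The second is precision. With only six subjects on placebo, it matters whether the first-NAC response is used, and how.

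**Working it through.** **Inputs from the documents.** 18 v 6; significance level 0.05 (sidedness is not stated, so two-sided is assumed); one NAC before and one after supplementation in every subject; the two named tests. The documents give no sample-size calculation, SD, effect size, correlation between the two NACs (rho) or visit effect, so there is no stated figure to reproduce. Those quantities are assumed below, with normal data.

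**Step 1. What the text permits.**

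- *Mann-Whitney on second-NAC values.* This is a randomised comparison, but it discards the first NAC.
- *Mann-Whitney on change.* This fits the sentence on differences from baseline, provided baseline means the first NAC. Appendix 4A also schedules nasosorption at 30 and 10 minutes before challenge on each NAC day, so baseline could equally mean the same-day sample. On that reading the first NAC is not used.
- *Within-arm Wilcoxon, before against after.* The data are paired and the objective is worded this way. Section 7 does not exclude it.

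For curettage, Appendix 4A schedules only the 8-hour sample, so gene expression has no same-day baseline. Its only challenge-day comparator within the subject is the first NAC, which Section 7 does not mention.

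**Step 2. The within-arm route.** The smallest two-sided exact signed-rank P with n = 6 is 2/2^6 = 0.031, and the next is 4/2^6 = 0.0625. The placebo arm is therefore significant only if all six changes have the same sign. With n = 18 the smallest P is 2/2^18 = 0.0000076.

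Simulation with 4,000 runs, no vitamin D effect, rho = 0.5, and the same visit shift in both arms. At this rho the within-subject difference has SD sqrt(2(1 − 0.5)) = 1, so shifts are in SDs of that difference.

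| Shift (SD) | Vitamin D arm P<0.05 | Placebo arm P<0.05 | Vitamin D only | Between-arm tests |
|---|---|---|---|---|
| 0 | 5% | 3% | 5% | about 5% |
| 0.25 | 18% | 4% | 17% | about 5% |
| 0.5 | 50% | 11% | 45% | about 5% |
| 0.75 | 82% | 22% | 64% | about 5% |

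The arms are independent, so the fourth column should equal the second times one minus the third. At 0.5 SD, 0.50 × (1 − 0.11) = 0.445, as found. A separate simulation at 0.3, 0.5 and 0.8 SD gave about 20, 44 and 67%. The between-arm tests are Mann-Whitney on the second NAC, Mann-Whitney on change, and ANCOVA. All hold their level because a shift common to both arms cancels.

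**Step 3. Precision of the between-arm routes.** With unit SD at each NAC, the SD per subject is 1 for the second NAC alone, sqrt(2(1 − rho)) for change and sqrt(1 − rho²) for ANCOVA. The standard error multiplies this by sqrt(1/18 + 1/6) = 0.471. The difference detectable with 80% power is (1.96 + 0.84) × SD × 0.471. Simulated power is for an assumed effect of 1 SD without a visit shift.

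| rho | SD: second / change / ANCOVA | Detectable difference (SD) | Simulated power |
|---|---|---|---|
| 0.3 | 1 / 1.183 / 0.954 | 1.32 / 1.56 / 1.26 | 49 / 37 / 54% |
| 0.5 | 1 / 1.000 / 0.866 | 1.32 / 1.32 / 1.14 | 49 / 48 / 63% |
| 0.7 | 1 / 0.775 / 0.714 | 1.32 / 1.02 / 0.94 | 48 / 72 / 79% |
| 0.8 | 1 / 0.632 / 0.600 | 1.32 / 0.84 / 0.79 | 48 / 86 / 91% |

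In the formula, the change score is worse than the second NAC alone whenever 2(1 − rho) > 1, that is, when rho is below 0.5.

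**Step 4. Small-sample correction.** Chance imbalance in the covariate inflates ANCOVA variance by about 1 + 1/(N − 4) = 1 + 1/20 = 1.05, so its standard error by sqrt(1.05) = 1.025. At rho = 0.5, 0.866 × 1.025 = 0.887, a gain of about 11% rather than 13%. At rho = 0.3, 0.954 × 1.025 = 0.978, a gain of about 2% over the second NAC alone. After this correction ANCOVA beats the second NAC alone when 1.05(1 − rho²) < 1, so rho above about 0.22, and beats change when 1.05(1 + rho) < 2, so rho below about 0.90.

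**The case against.** A reader might infer that the plan must either ignore the first NAC or test within arms. The documents do not support that. The sentence after the named tests plans the difference from baseline compared between active and placebo. A Mann-Whitney on change from the first NAC fits that sentence, uses the first-NAC data and cancels a common visit effect.

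A reader might also infer that the sponsor intends to conclude from a result significant in one arm only. Nothing says so. The trial is randomised and placebo-controlled, Section 7 frames its tests as comparisons with placebo, and the objective may only describe when samples are taken.

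The visit effect is itself an assumption, and the design limits some sources of it: testing is in winter, outside the pollen season, at about 9 AM and 28 to 35 days apart. Choosing ANCOVA over a change score is a matter of efficiency, and the gain depends on an unknown correlation and on roughly linear, normal data, whereas Section 7 expects mediators to be non-normal.

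All of this stands as a limit on the point. It does not close the gap. Baseline is undefined, no test is attached to the ViDAR contrast, and the framing sentence speaks of challenge effects against placebo. In ViDAR both arms receive allergen and the placebo is an oral one, so that sentence does not clearly describe this trial.

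**Conclusion.** The point holds as a gap with a cheap improvement, not as an error in the tests named. Section 7 leaves the vitamin D contrast unspecified and names no baseline-adjusted analysis, although every subject has a first NAC.

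The risk of crediting vitamin D with a visit effect belongs to the within-arm route alone: about 20, 44 and 67% of trials at assumed shifts of 0.3, 0.5 and 0.8 SD of the within-subject difference. It would be wrong to extend that bias to the Mann-Whitney comparisons, which stay near 5%; their weakness is precision.

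Against them, ANCOVA reduces the standard error by roughly 11 to 13% at an assumed rho of 0.5, and by only about 2% relative to the second NAC alone at 0.3 once small-sample imbalance is counted. All sizes rest on assumed normal data, visit shifts, correlation and a 1 SD effect, none of which the documents supply. The change should be made because it settles which contrast carries the conclusion, whatever the correlation turns out to be.

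**What to change.** Add to Section 7:

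> For ViDAR, baseline is the same subject's first-NAC response. The vitamin D effect is the between-arm difference in second-NAC response (log scale), estimated by ANCOVA with the first-NAC value as covariate and reported with a 95% CI. If residuals are clearly non-normal, rank ANCOVA or Mann-Whitney on change from the first NAC will be used. Within-arm before/after tests are descriptive and will not support a vitamin D conclusion.

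The cost is a few lines of text and no new data or visits. One residual degree of freedom is spent (22 to 21), and chance baseline imbalance at N = 24 costs about 2.5% in standard error, which would be a small net loss only if the two NAC responses were nearly uncorrelated.

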APPENDIX 2A

Appendix 2A

Nasal Challenge with TLR Agonists:

Poly-IC or poly-ICLC (TLR3) or Resiquimod (TLR7/8) or MPLA (TLR4)

[figure not shown]
Part A: Incremental Ascending Dose Study based on Tolerability and SAM

4 Cohorts of 8 Healthy Volunteers (4 atopic; 4 non-atopic) *One cohort per agonist*
Each subject given saline control and 3 ascending doses

Safety & Dosing Tolerability

Nasal mucosa examination, nasal & systemic symptoms checked at all timepoints

- 1st subject challenged (observed for 8h)
- If dose well tolerated, 2nd & 3rd subjects challenged (observed until 8h)
- If dose well tolerated, then subjects 4-8 challenged (observed until 8h)

UPDATE FEB 2016: RESIQUIMOD WILL NOT BE GIVEN AT A HIGHER DOSE THAN 10µg/100µl PER NOSTRIL

[figure not shown]

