In nasal micro-curettage samples it is possible to measure gene expression, which assesses levels of thousands of mRNA molecules. The [name] group has recently found that there are profound changes in circadian-associated genes in the nasal mucosa after NAC, and that these genes are inhibited by corticosteroids. Circadian genes regulate innate aspects of the immune system by actions involving the BMAL1-CLOCK complex of nuclear transcription factors, receptors and enzymes (70) (71;72). The circadian clock was first identified with regard to lipopolysaccharide(LPS) responses varying with the time of the day, and these circadian responses have been shown to be present in murine macrophage responses to endotoxin (73;74) and more recently in murine inflammatory monocytes (75). In addition, a bronchiolar epithelial clock controls pulmonary inflammation and glucocorticoid action in mice, as shown by genetic ablation of the mouse clock gene *Bmal1* in bronchiolar epithelial cells (76).

Our demonstration in the human nose of allergen-induced changes in circadian-associated genes in the presence of innate inflammatory pathways, suggests that the circadian-associated genes could be controlling gene expression and protein synthesis involved in these innate inflammatory pathways. Furthermore, these allergen-induced circadian changes are reversed by a single preceding oral dose of prednisone, consistent with

known actions of endogenous cortisol (77) (76) implying that the corticosteroid may be acting on circadian-associated genes in order to resolve inflammation.

Since the NAC model with grass pollen is exquisitely sensitive to studying the effects of therapy, we have designed a clinical study to assess whether vitamin D supplementation can alter NAC responses through effects on circadian-associated genes and pathways of inflammation in asthma (78). After a review of the literature we propose a dose of 4000 IU per day for 4 weeks, since this level of dietary supplementation has been safely used in pregnant women and in a large clinical study in asthma (79;80) (65). We shall assess whether there are effects of vitamin D on inflammation produced after NAC: looking at levels of cytokines, chemokines, cells and gene expression, with a focus on circadian-associated genes (78).

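### Section 7 gives ViDAR no analysis of its own: 12 post-challenge samples are each tested at P<0.05 without multiplicity control, and the lead outcome, baseline, AUC window and role of the first challenge are not fixed

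*Combined protocol and SAP*

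**What the plan says.** Section 7 is one analysis text for every challenge arm. ViDAR appears in it only under Randomization, which covers supervision by the pharmacy and custody of the codes.

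- **Testing rule.** "Non-parametric tests are used to compare challenge effects with placebo at different times", with Wilcoxon signed-rank for paired and Mann-Whitney for unpaired data. "The differences from baseline and difference compared with that from placebo (active-placebo) at each time point" are to be calculated and their significance determined. The threshold is P<0.05. No multiplicity rule is given.
- **Outcome.** Section 7 states: "The major data will be levels of cytokines and chemokines in nasal SAM eluates". The ViDAR rationale in Section 1.2 describes "looking at levels of cytokines, chemokines, cells and gene expression, with a focus on circadian-associated genes". The ViDAR objective in Section 2.1 lists mediators and circadian gene expression together, unranked.
- **AUC.** Areas are obtained "by selecting specified times in the early or late phase or for the entire response", with two illustrations: "e.g. PGD2 from 10min to 2h" and "e.g. for IL-4 at 4 to 8h".
- **Design.** Section 3 (Group 3 Part A) randomises 24 subjects, 18 to vitamin D and 6 to placebo, with one allergen challenge (NAC) before and one after supplementation. Section 6 describes the placebo as an oral product made to resemble the vitamin D.
- **Sampling.** Appendix 4A takes nasosorption at -30m and -10m, with a bilateral lavage at -20m between them. Post-challenge samples follow at 5, 15, 30 and 45 minutes, 1 hour, and hourly from 2 to 8 hours. Curettage is done once per challenge day, at 8 hours.

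**The concern.** The general text was not adapted to the one randomised, placebo-controlled supplementation comparison in the study. In other arms the comparator is a challenge; in TLR Part A, for example, "Each subject given saline control and 3 ascending doses". In ViDAR every subject receives allergen at both challenges and placebo is the oral arm, so a rule that compares challenge effects with placebo does not describe the vitamin D question.

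Two things are at stake. First, testing each time point at 0.05 gives a false-positive rate per mediator well above 5%. If the outcome, baseline or window is also settled after the codes are released, a chance difference can be reported as a vitamin D effect. Second, the first-challenge result is planned for every subject but has no stated role in the between-arm test. With only six placebo subjects, ignoring it or using it badly can cost power.

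**Working it through.** The documents give no power, effect size, SD or correlation for ViDAR, so there is no figure to reproduce. Correlations and the 1 SD effect below are assumptions. Tests are taken as two-sided (the plan does not say). Simulations use 18 v 6, the exact Mann-Whitney test and 20,000 trials per setting unless stated.

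**1. Number of tests.** Appendix 4A: 5m, 15m, 30m, 45m, 1h (5) + hourly 2-8h (7) = 12 per mediator per challenge day.

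**2. Ceiling under independence.** 1 - 0.95^12 = 0.460. The exact Mann-Whitney test at 18 v 6 has attained size 0.0472, so 1 - (1 - 0.0472)^12 = 0.440.

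**3. With correlated time points, no effect, one mediator:**

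| Assumed correlation | At least one P<0.05 | At least one after Benjamini-Hochberg over the 12 |
|---|---|---|
| AR(1) 0.5 | 39.6% | 4.2% |
| AR(1) 0.7 | 34.3% | 3.7% |
| AR(1) 0.9 | 22.4% | 2.9% |
| AR(1) 0.95 | 16.7% | 2.9% |
| Exchangeable 0.5 | 32.2% | 3.6% |
| Exchangeable 0.7 | 23.9% | 3.2% |
| Exchangeable 0.9 | 14.6% | 2.6% |

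A second run gave 40.8% for AR(1) 0.5 and 14.2% for exchangeable 0.9. The range is about 14-40%.

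**4. More mediators.** The plan does not give their number. If 5: 5 x 12 = 60 tests, and 60 x 0.05 = 3 expected false positives. If 10: 120 tests and 6 expected.

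**5. Open choices on a single AUC, no effect.** Taking the best of three windows (5m-2h, 4-8h, 5m-8h) gives P<0.05 in 6-11% of trials. Taking the best of three baselines on one AUC (same-day -30m, same-day -10m, first NAC) gives 11-13%. The baseline figure assumes visit correlation 0.3-0.7, AUC to pre-challenge correlation 0.3-0.5, and -30m to -10m correlation 0.5-0.8.

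**6. Use of the first NAC: power for a 1 SD effect.**

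| Data, visit correlation | Mann-Whitney, second NAC only | Mann-Whitney, change | Rank ANCOVA | ANCOVA |
|---|---|---|---|---|
| Normal, 0.3 | 49.1% | 37.5% | 51.6% | 54.7% |
| Normal, 0.5 | 48.9% | 48.8% | 58.4% | 62.8% |
| Normal, 0.7 | 48.8% | 70.2% | 71.7% | 79.0% |
| t (4 df), 0.3 | 61.5% | 48.3% | 64.1% | 60.4% |
| t (4 df), 0.5 | 61.9% | 61.5% | 71.2% | 68.8% |
| t (4 df), 0.7 | 61.8% | 80.5% | 82.3% | 82.5% |

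- Rank ANCOVA minus the better Mann-Whitney option is +2.5, +9.5 and +1.5 points (normal) and +2.6, +9.3 and +1.8 points (t): about 2-9 points.
- Outside that range it does not help. At correlation 0 (normal) it has 48.1% against 48.9% for second NAC only. At 0.9 it trails change, 96.3% against 99.0% (normal) and 97.7% against 98.9% (t).
- Cost of the worse Mann-Whitney option, normal: 49.1 - 37.5 = 11.6 points at 0.3; 48.9 - 48.8 = 0.1 at 0.5; 70.2 - 48.8 = 21.4 at 0.7. That is 0-21 points.

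**7. Why before/after tests within arms cannot carry the conclusion.** The smallest two-sided signed-rank P with n=6 is 2/2^6 = 0.031. If both arms truly change by the same 0.5, 0.7 or 0.9 SD of the differences, the vitamin D arm is significant and the placebo arm is not in 44%, 66% and 66% of trials (4,000 runs each).

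**The case against.** The strongest reply is that ViDAR is titled mechanistic, no arm declares a primary outcome, and no confirmatory claim is made. That limits what is at stake and makes an exploratory label a legitimate answer. It does not remove the point: Section 7 calls P<0.05 significant and carries no such label.

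Several stronger readings are tempting, and the documents do not support them.

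- *Two conflicting primary outcomes.* No primary is declared. Section 7 speaks of the whole study and Section 1.2 of ViDAR. The difference is one of emphasis, and the gap is that no lead is named.
- *Placebo cannot be identified.* Sections 3 and 6 make clear that it is the oral arm, and Appendix 4A has no saline challenge. Only the Section 7 wording fails to fit.
- *The choice of test is wholly open.* Vitamin D versus placebo is a parallel-arm contrast, so the unpaired test applies. What stays open is whether it uses the second challenge alone or the change.
- *The PGD2 window is an error.* It is a general example, and 10 minutes is a sampling time in Appendix 4B. It is simply not one in Appendix 4A.
- *Multiplicity spares the gene data.* Repeated time points do not arise there, but Section 1.2 says curettage measures thousands of mRNA molecules.

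On size, the 40% end needs a correlation between the 5-minute and 8-hour samples of 0.5^11, about 0.0005. That sits badly with visit correlations of 0.3-0.7. Adding a persistent subject component of 0.3-0.7 narrows the range to about 17-34%, still well above 5%.

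**Conclusion.** The concern holds. Followed as written, the per-time-point rule gives at least one false-positive result for a single mediator in about 14-40% of trials with no vitamin D effect, against about 3-4% with Benjamini-Hochberg. These rates rest on assumed within-day correlations, because the documents give none. Testing more mediators or genes adds to them. The unnamed lead outcome, the three possible baselines and the example-only AUC windows leave further room for selection after unblinding.

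The missing role for the first challenge is a smaller matter. At visit correlation 0.3-0.7 and a 1 SD effect, rank ANCOVA gains about 2-9 points of power over the better Mann-Whitney option. It gains nothing near correlation 0 and loses 1-3 points at 0.9. Picking the worse Mann-Whitney option costs 0-21 points over 0.3-0.7. A reader might infer that a large loss is certain, but at correlation 0.5 it is essentially nil.

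**What to change.** Add a ViDAR paragraph to Section 7, fixed before the codes are released:

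1. Name one lead outcome: the AUC of one mediator over one window built from Appendix 4A times (4-8h is one that fits), or one circadian gene or gene score at 8 hours.
2. Test vitamin D against oral placebo on the second-NAC value with the same subject's first-NAC value as covariate, by rank ANCOVA or by ANCOVA on the log scale. Name one. Rank ANCOVA suits the non-normal levels that Section 7 expects.
3. Name the same-day sample (-30m, -10m or their mean) used for within-day change, and state that placebo in ViDAR means the oral arm.
4. Control the false discovery rate over the remaining mediators, time points and genes, or label them exploratory.
5. Keep the before/after comparison in Section 2.1 as a reported result, but base the vitamin D conclusion on the between-arm test.

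The cost is one paragraph and a little analysis code, with no new samples, visits or subjects. The downsides are fewer nominally significant results, a commitment to one lead outcome, and less weight on the within-arm tests.

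Fallback: label all of ViDAR exploratory and drop the P<0.05 rule for it. This settles multiplicity at lower cost but gives up any confirmatory vitamin D claim, and item 3 is still needed.
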